7.3 Medical Monitoring

It is the responsibility of the Principal Investigator to oversee the safety of the study at his/her site. This safety monitoring will include careful assessment and appropriate reporting of adverse events as noted above, as well as the construction and implementation of a site data and safety-monitoring plan (see section 9 Auditing, Monitoring and Inspecting). Medical monitoring will include a regular assessment of the number and type of serious adverse events.

8.0 STATISTICAL ANALYSIS PLAN

This is a stratified phase I trial with 2 phases: a safety phase and an expansion phase.

Safety Phase: Pembrolizumab is fixed. Two radiotherapy fractionation schedules are tested: 8 Gy x 3 and 17 Gy x 1. Patients are stratified by prior PD-1 therapy. 24 patients will be enrolled, 12 per stratum and 6 per fractionation cohort.

Table 11

	Progressed on Prior PD-1 (Melanoma or NSCLC)	Cohort 1: 8 Gy x 3 Number of Patients	Cohort 2: 17 Gy x 1 Number of Patients	TOTAL
		6	6	

May 3, 2017

Confidential  Limited Access

Stratify	No Prior PD-1 (Pancreas, Breast or Other cancers)	6	6*	12
	TOTAL	12	12	24
	* Breast or Other cancer patients only			

Safety Phase Decision-making: Dose limiting toxicity (DLT) is defined in Sections 2.1 and 5.2. The regimen is considered safe if 0-1 DLTs are observed in 6 patients within a stratum. Stop if 2+ DLT at any time. If 2+ DLT in Cohort 1, then Cohort 2 will still be tested. Cohort 1 → Cohort 2 is not an escalation of dose.

Expansion Phase: Patients are now stratified by disease site.

- If both fractionation regimens are considered safe for both prior PD-1 therapy strata, then we will randomize patients. Randomization will aid in our preliminary assessment of clinical response by avoiding selection bias. Although unlikely, if only one of the fractionation regimens is considered safe for both prior PD-1 therapy strata, then all patients will be enrolled on the fractionation regimen which was determined to be safe.

Table 12

Disease	Randomize		Number of Randomized Patients
	Cohort 1: 8 Gy x 3 Number of Patients	Cohort 2: 17 Gy x 1 Number of Patients	
Melanoma	7	7	14
NSCLC	7	7	14
Pancreas	6	0	6*
Breast	3	3	6
Other cancers	3	3	6
TOTAL	26	20	46
	* Pancreas patients are not randomized, they are assigned to 8 Gy x 3		

Expansion Phase Decision-making: We will first evaluate response rate by fractionation cohort. We will pool all disease sites. This is a global assessment of RADVAX™ by fractionation cohort. Of 38 patients in cohort 1, 26 (68%) and of 32 patients in cohort 2, 20 (63%) will have been randomized to treatment in the expansion phase, which strengthens any comparative conclusions, although preliminary. Immune PD markers will also be examined by fractionation cohort.

Table 13

	Cohort 1: 8 Gy x 3 Number of Patients	Cohort 2: 17 Gy x 1 Number of Patients	STUDY TOTAL
Safety phase	12	12	24
Expansion phase	26	20	46
TOTAL	38	32	70

The following are examples of response rates and exact 95% CIs based on 38 patients in Cohort 1 and 32 patients in Cohort 2.

Table 14

Cohort 1			Cohort 2		
N= 38 patients			N = 32 patients		
# Respond	Response Rate	95% exact CI	# Respond	Response Rate	95% exact CI
5	13.2%	4.4 – 28.1%	4	12.5%	3.5 – 29.0
10	26.3%	13.4 – 43.1%	8	25.0%	11.5 – 43.4
19	50.0%	33.4 – 66.6%	16	50.0%	31.9 – 68.1
30	78.9%	62.7 – 90.4%	24	75.0%	56.6 – 88.5
35	92.1%	78.6 – 98.3%	28	87.5%	71.0 – 96.5

Next we will evaluate response rate by disease site. Here we pool fractionation cohorts. This is an assessment of RADVAX™ activity by disease, although preliminary.

Table 15

Disease	Safety Phase (Number is expected not required**)	Expansion Phase (Number is required)	STUDY TOTAL
Melanoma	6	14	20
NSCLC	6	14	20
Pancreas	4	6	10
Breast	4	6	10
Other cancers	4	6	10

** assumes equal numbers by disease strata in (12 prior PD-1 and 12 no prior PD-1)

For Melanoma and NSCLC cohorts: If 0/14 in the expansion phase respond then we can rule out a 20% response rate with 95% confidence. If 0/20 (pooling both phases) respond, then we can rule out a 15% response rate with 95% confidence.

For Pancreas, breast cancer and other cancers: If 0/6 in the expansion phase respond then we can rule out a 40% response rate with 95% confidence. If 0/10 (pooling both phases) respond, then we can rule out a 27% response rate with 95% confidence.

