5.2 Trial Treatments

The treatment to be used in this trial is outlined below in Tables 2 and 3

Table 2 Pembrolizumab Treatment

Drug	Dose/Potency	Dose Frequency	Route of Administration	Regimen/Treatment Period	Use
Pembrolizumab	200 mg	Every 3 weeks	IV infusion	6 three week cycles*	Experimental
The PEMBROLIZUMAB dosing interval may be increased due to toxicity as described in Section 5.2.1.2.					

Pembrolizumab should be administered 7 days (+/- 3 days) prior to the first fraction of hypofractionated radiation.

*NOTE: Patients who have stable or responding disease and are felt to be clinically benefiting from the drug can continue receiving pembrolizumab for up to 2 years. For cancers not currently commercially approved for treatment with pembrolizumab, the drug will be provided by Merck.

In the initial ***Safety Phase***, there will be two cohorts of patients based upon the radiotherapy dose delivered to the index metastatic lesion in the lung, liver, bone or soft tissue:

Cohort 1: 8 Gy x 3 to the index lesion

Cohort 2: 17 Gy x 1 to the index lesion*

*Subjects with locally advanced pancreatic cancer will be enrolled only in the 8 Gy x 3 cohort.

Patients are stratified by prior PD-1 therapy. 24 patients will be enrolled, 12 per stratum and 6 per fractionation cohort within each stratum. Standard safety decision-making will be used. The regimen is safe if no more than 0-1 dose-limiting toxicities (DLT) are observed in 6 patients within a cohort within a stratum. Enrollment in a cohort within a stratum will stop if 2+ DLT are observed within that cohort at any time during the safety phase. If 2+ DLT are observed in Cohort 1 in a stratum, then Cohort 2 within that stratum will still be tested. Cohort 1 → Cohort 2 is **not** an escalation of dose. DLT is defined as any Grade 3 or higher non-hematological toxicity and any Grade 4 hematological toxicity that is probably, possibly or definitely related to the combination of Pembrolizumab and hypofractionated radiotherapy.

Table 3. Hypofractionated Radiotherapy

Safety Phase:

Stratify	Progressed on Prior PD-1 (Melanoma or NSCLC) No Prior PD-1 (Pancreas, Breast or Other)	Cohort 1: 8 Gy x 3 → Cohort 2: 17 Gy x 1		TOTAL
		Number of Patients	Number of Patients	
		6	6	12
		6	6*	12
TOTAL		12	12	24
* Breast or Other cancer patients only				

Expansion Phase

Disease	Randomize		Number of Randomized Patients
	Cohort 1: 8 Gy x 3	Cohort 2: 17 Gy x 1	
Melanoma	7	7	14
NSCLC	7	7	14
Pancreas	6	0	6*
Breast	3	3	6

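### The SAP counts six assigned pancreas patients as randomised (Cohort 1 is 20/38 = 53%, not 68%), and its pooled comparison of fractionation cohorts mixes disease site with regimen

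*Combined protocol and SAP*

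**What the plan says.** Under Expansion Phase Decision-making in Section 8.0, the SAP sets out its first efficacy analysis: "We will first evaluate response rate by fractionation cohort", and "We will pool all disease sites". It then gives the share of each cohort that is randomised: "Of 38 patients in cohort 1, 26 (68%) and of 32 patients in cohort 2, 20 (63%) will have been randomized to treatment". It says of this share: "which strengthens any comparative conclusions, although preliminary". The response-rate examples in Table 14 are "based on 38 patients in Cohort 1 and 32 patients in Cohort 2", so the pooled denominators cover both phases and every site.

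Table 12, just above that text, puts 6 pancreas patients in Cohort 1 and none in Cohort 2. Its footnote reads: "Pancreas patients are not randomized, they are assigned to 8 Gy x 3". Table 3 in Section 5.2 carries the same footnote. Both tables nevertheless list these six in the column of randomised patients, which totals 46.

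In the safety phase, the no-prior-PD-1 cell of Cohort 2 is footnoted "Breast or Other cancer patients only" (Table 3, repeated in Table 11). Table 15 expects 4 pancreas patients in the safety phase and marks that number as expected rather than required.

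The only analysis by disease site pools the two fractionation cohorts. No comparison of regimens that is stratified by site, adjusted for site or limited to randomised patients is described.

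**The concern.** The sentence on the randomised share and the footnote above it cannot both be right. The sentence matters because it is the SAP's stated reason for giving weight to a comparison of the regimens. Sections 2.1, 5.2, 5.3 and 8.0 all say that randomisation is there to avoid selection bias.

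The six miscounted patients also share one disease, and that disease appears in one cohort only. If pancreatic cancer responds differently from the other sites, the pooled rates will differ between cohorts even when the regimens are equivalent. The by-site analysis cannot remove this, because it merges the regimens. Response in non-index lesions is the trial's only secondary objective. Immune pharmacodynamic markers are also to be examined by fractionation cohort, so they inherit the same imbalance.

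**Working it through.** **Inputs.** Expansion allocation from Table 12 (Cohort 1 / Cohort 2): melanoma 7/7, NSCLC 7/7, pancreas 6/0, breast 3/3, other 3/3. Cohort totals from Table 13: 12 + 26 = 38 and 12 + 20 = 32. Expected safety-phase mix from Tables 11 and 15: 12 melanoma or NSCLC split 6/6, and 4 each of pancreas, breast and other, with no pancreas in Cohort 2.

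**1. The plan's own figure.**
- Cohort 1: 7 + 7 + 6 + 3 + 3 = 26, and 26/38 = 68.4%.
- Cohort 2: 7 + 7 + 0 + 3 + 3 = 20, and 20/32 = 62.5%.

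The stated 68% and 63% are reproduced, but the 68% only if the six pancreas patients count as randomised.

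**2. The count under the footnote.**
- Cohort 1: 26 - 6 = 20, and 20/38 = 52.6%.
- Cohort 2: unchanged at 62.5%.
- Overall: 40/70 = 57.1%, not 46/70 = 65.7%.

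The order of the cohorts reverses: Cohort 1 is the less randomised of the two.

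**3. Expected disease mix of the pooled cohorts.**

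| | Cohort 1 (n = 38) | Cohort 2 (n = 32) |
|---|---|---|
| Melanoma or NSCLC | 6 + 14 = 20 (53%) | 6 + 14 = 20 (63%) |
| Breast or other | 2 + 6 = 8 (21%) | 6 + 6 = 12 (38%) |
| Pancreas | 4 + 6 = 10 (26%) | 0 |

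The safety phase could bring 0 to 6 pancreas patients into Cohort 1, so the pancreas total could be 6 to 12 of 38 (16% to 32%).

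**4. Difference produced by mix alone.** Suppose the regimens are equivalent, every non-pancreas site responds at rate r, and pancreas responds at rate q. With k pancreas patients in Cohort 1:

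Cohort 1 minus Cohort 2 = [(38 - k)r + kq]/38 - r = (k/38)(q - r)

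The documents give no response rates for this combination, so r and q are assumptions.

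| r | q | k = 6 | k = 10 (expected) | k = 12 |
|---|---|---|---|---|
| 20% | 0% | -3.2 | -5.3 | -6.3 |
| 30% | 0% | -4.7 | -7.9 | -9.5 |
| 40% | 0% | -6.3 | -10.5 | -12.6 |
| 20% | 5% | -2.4 | -3.9 | -4.7 |
| 30% | 5% | -3.9 | -6.6 | -7.9 |
| 40% | 5% | -5.5 | -9.2 | -11.1 |

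Entries are percentage points. For example, with r = 20%, q = 0% and k = 10, Cohort 1 is 28 x 0.20/38 = 14.7% against 20.0% in Cohort 2.

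**5. What the randomised comparison looks like.** The 40 randomised patients are split 7/7, 7/7, 3/3 and 3/3. Mantel-Haenszel weights for a risk difference are 7 x 7/14 = 3.5 (twice) and 3 x 3/6 = 1.5 (twice), which sum to 10. These are proportional to the site sizes, so with complete data the stratified estimate equals the simple 20 v 20 difference, and site mix contributes nothing to it.

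**The case against.** The strongest reply concedes the count and disputes how much it matters.

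- **Role of the figure.** The primary endpoint is dose-limiting toxicity. The randomised share enters no sample size, stopping rule or confidence interval, and 38 and 32 are correct as cohort sizes. The SAP plans no between-cohort test and calls its comparative conclusions preliminary. All of this stands, and it limits the consequence to interpretation. But the preliminary label speaks to certainty. It does not correct a wrong count or tell the reader that one disease sits in one cohort only.
- **Disclosure.** The footnotes and the 6/0 row show the pancreas allocation openly, and the SAP does not claim that the 24 safety-phase patients were randomised. That is true, and it is why the sentence contradicts the SAP's own table.
- **Partial confounding.** Four of the five expansion sites are split 1:1. This stands. The imbalance is pancreas, plus the matching shift of breast and other patients in the safety phase.
- **Fragile size.** The response rates are assumed, and a single rate for all non-pancreas sites is a simplification. With 5% in melanoma or NSCLC, 20% in breast or other and 5% in pancreas (also assumed), the rates are (1.0 + 1.6 + 0.5)/38 = 8.2% and (1.0 + 2.4)/32 = 10.6%, a gap of -2.5 points. Sampling error is also larger than the bias: at a 20% rate, 1.96 x sqrt(0.16/38 + 0.16/32) is about 19 points. Both points stand. Neither removes a systematic difference that the plan can avoid at no cost.
- **Text against tables.** Sections 2.1 and 5.2 restrict only locally advanced pancreatic cancer to 8 Gy x 3, while the footnotes to Tables 3, 11 and 12 keep all pancreas patients out of Cohort 2. The working follows the tables. These passages must be reconciled.

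**Conclusion.** The concern holds. On the SAP's own Table 12, 20 of 38 Cohort 1 patients (53%) are randomised, not 26 (68%), and 40 patients in all, not 46. This part needs no assumption beyond the planned enrolment and both regimens being found safe, which is the condition for randomising at all.

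The pooled 38 v 32 comparison partly confounds regimen with disease site, with an expected 26% pancreas (range 16% to 32%) against none. At the expected mix, the resulting difference is 3.9 to 10.5 points against Cohort 1 for assumed response rates of 20% to 40% in non-pancreas sites and 0% or 5% in pancreas. It would be smaller under some other patterns, and it would reverse if pancreas responded better than the rest. What is affected is the reading of the secondary response endpoint and of the immune markers by cohort. The safety conclusion and the sample size are untouched.

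**What to change.** 1. In Section 8.0, replace the randomised shares with 20 (53%) of 38 and 20 (63%) of 32. In Tables 3 and 12, show 40 randomised plus 6 assigned instead of 46 randomised.
2. State that any comparison between fractionation regimens, for response or immune markers, uses the 40 randomised patients (20 v 20), stratified by disease site. For response, a Mantel-Haenszel or exact stratified risk difference with its interval would do. With full 7/7 and 3/3 splits the Mantel-Haenszel estimate is the simple difference; stratifying protects it if evaluable numbers become uneven within a site.
3. Keep the pooled 38 and 32 rates as description within each cohort, and show Cohort 1 also without pancreas.
4. Reconcile the Sections 2.1 and 5.2 text on which pancreatic cancer patients are limited to one cohort with the table footnotes, since the count of randomised patients depends on it.

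The cost is a few lines of SAP text and one extra estimate, with no change to enrolment, treatment or visits. The price is precision: 5/20 (25%) has an exact 95% interval of about 9% to 49%, against 11.5% to 43.4% for 8/32 in Table 14. The stated randomised share also becomes less favourable.

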9.0 LABELING, PACKAGING, STORAGE AND RETURN OF CLINICAL SUPPLIES

9.1 Investigational Product

The investigator shall take responsibility for and shall take all steps to maintain appropriate records and ensure appropriate supply, storage, handling, distribution and usage of investigational product in accordance with the protocol and any applicable laws and regulations.

Clinical Supplies will be provided by Merck as summarized in Table 16.

Table 16 Product Description

Product Name & Potency	Dosage Form
PEMBROLIZUMAB 100 mg/ 4mL	Solution for Injection

9.2 Packaging and Labeling Information

Clinical supplies will be affixed with a clinical label in accordance with regulatory requirements.

9.3 Clinical Supplies Disclosure

This trial is open-label; therefore, the subject, the trial site personnel, the Sponsor and/or designee are not blinded to treatment. Drug identity (name, strength) is included in the label text; random code/disclosure envelopes or lists are not provided.

9.4 Storage and Handling Requirements

Clinical supplies must be stored in a secure, limited-access location under the storage conditions specified on the label.

Receipt and dispensing of trial medication must be recorded by an authorized person at the trial site.

Clinical supplies may not be used for any purpose other than that stated in the protocol.

9.5 Returns and Reconciliation

The investigator is responsible for keeping accurate records of the clinical supplies received from Merck or designee, the amount dispensed to and returned by the subjects and the amount remaining at the conclusion of the trial.

Upon completion or termination of the study, all unused and/or partially used investigational product will be destroyed at the site per institutional policy. It is the Investigator's responsibility to arrange for disposal of all empty containers, provided that procedures for proper disposal have been established according to applicable federal, state, local and institutional guidelines and procedures, and provided that appropriate records of disposal are kept.

10.0 ADMINISTRATIVE AND REGULATORY DETAILS

10.1 Compliance with Trial Registration and Results Posting Requirements

Under the terms of the Food and Drug Administration Modernization Act (FDAMA) and the Food and Drug Administration Amendments Act (FDAAA), the Sponsor of the trial is solely responsible for determining whether the trial and its results are subject to the requirements for submission to the Clinical Trials Data Bank, <http://www.clinicaltrials.gov>. Information posted will allow subjects to identify potentially appropriate trials for their disease conditions and pursue participation by calling a central contact number for further information on appropriate trial locations and trial site contact information.

11.0 DATA HANDLING AND RECORD KEEPING

11.1 Confidentiality

Information about study subjects will be kept confidential and managed according to the requirements of the Health Insurance Portability and Accountability Act of 1996 (HIPAA). Those regulations require a signed subject authorization informing the subject of the following:

- What protected health information (PHI) will be collected from subjects in this study
- Who will have access to that information and why
- Who will use or disclose that information
- The rights of a research subject to revoke their authorization for use of their PHI.

In the event that a subject revokes authorization to collect or use PHI, the investigator, by regulation, retains the ability to use all information collected prior to the revocation of subject authorization. For subjects that have revoked authorization to collect or use PHI, attempts should be made to obtain permission to collect at least vital status (i.e. that the subject is alive) at the end of their scheduled study period.

11.2 Source Documents

Source data is all information, original records of clinical findings, observations, or other activities in a clinical trial necessary for the reconstruction and evaluation of the trial. Source data are contained in source documents. Examples of these original documents, and data records include: hospital records, clinical and office charts, laboratory notes, memoranda, subjects' diaries or evaluation checklists, pharmacy dispensing records, recorded data from automated instruments, copies or transcriptions certified after verification as being accurate and complete, microfiches, photographic negatives, microfilm or magnetic media, x-rays, subject files, and records kept at the pharmacy, at the laboratories, and at medico-technical departments involved in the clinical trial.

11.3 Case Report Forms

The study case report form (CRF) is the primary data collection instrument for the study. All data requested on the CRF must be recorded. All missing data must be explained. If a space on the CRF is left blank because the procedure was not done or the question was not asked, write "N/D". If the item is not applicable to the individual case, write "N/A". All entries should be printed legibly in black ink. If any entry error has been made, to correct such an error, draw a single straight line through the incorrect entry and enter the correct data above it. All such changes must be initialed and dated. DO NOT ERASE OR WHITE OUT ERRORS. For clarification of illegible or uncertain entries, print the clarification above the item, then initial and date it.

11.4 Records Retention

It is the investigator's responsibility to retain study essential documents for at least 2 years after the last approval of a marketing application in their country and until there are no pending or contemplated marketing applications in their country or at least 2 years have elapsed since the formal discontinuation of clinical development of the investigational product.

12.0 ETHICAL CONSIDERATIONS

This study is to be conducted according to US and international standards of Good Clinical Practice (FDA Title 21 part 312 and International Conference on Harmonization guidelines), applicable government regulations and Institutional research policies and procedures.

This protocol and any amendments will be submitted to a properly constituted independent Ethics Committee (EC) or Institutional Review Board (IRB), in agreement with local legal prescriptions, for formal approval of the study conduct. The decision of the EC/IRB concerning the conduct of the study will be made in writing to the investigator and a copy of this decision will be provided to the sponsor before commencement of this study. The investigator should provide a list of EC/IRB members and their affiliate to the sponsor.

All subjects for this study will be provided a consent form describing this study and providing sufficient information for subjects to make an informed decision about their participation in this study. See attachment for a copy of the Subject Informed Consent Form. This consent form will be submitted with the protocol for review and approval by the

EC/IRB for the study. The formal consent of a subject, using the EC/IRB-approved consent form, must be obtained before that subject undergoes any study procedure. The consent form must be signed by the subject, and the investigator-designated research professional obtaining the consent.

13.0 STUDY FINANCES

13.1 Funding Source

This study will be supported with funds from Merck, Inc. and internal funds from the Department of Radiation Oncology.

13.2 Conflict of Interest

Any investigator who has a conflict of interest with this study (patent ownership, royalties, or financial gain greater than the minimum allowable by their institution, etc.) must have the conflict reviewed by a properly constituted Conflict of Interest Committee with a Committee-sanctioned conflict management plan that has been reviewed and approved by the study sponsor prior to participation in this study. All University of Pennsylvania investigators will follow the University conflict of interest policy.

14.0 PUBLICATION PLAN

Neither the complete nor any part of the results of the study carried out under this protocol, nor any of the information provided by the sponsor for the purposes of performing the study, will be published or passed on to any third party without the consent of the study sponsor. Any investigator involved with this study is obligated to provide the sponsor with complete test results and all data derived from the study. Rule regarding the publication of results from this study are covered in the sponsored research agreement between Merck and the University of Pennsylvania.

